11.0 Management and Reporting of Complaints

A Complaint is any written, electronic, or oral communication that alleges deficiencies related to the physical characteristics, identity, quality, purity, potency, durability, reliability, safety, effectiveness, or performance of a product/device after it is released for distribution.

The investigational product in this trial contains both:

- Biologic compound(s) and
- Device component(s) (pre-filled syringe, pen).

Complaints associated with any component of this investigational product must be reported to the Sponsor (Section 11.2.2). For adverse events, please refer to Sections 11.1.1 through 11.1.6. For product complaints, please refer to Section 11.2

11.1 Medical Complaints

11.1.1 Adverse Event Definition and Serious Adverse Event Categories

An adverse event (AE) is defined as any untoward medical occurrence in a patient, which does not necessarily have a causal relationship with their treatment. An adverse event can therefore be any unfavorable and unintended sign (including an abnormal laboratory finding), symptom, or disease temporally associated with the use of a medicinal product, whether or not the event is considered causally related to the use of the product.

Such an event can result from use of the drug as stipulated in the labeling, as well as from accidental or intentional overdose, drug abuse, or drug withdrawal. Any worsening of a pre-existing condition or illness is considered an adverse event.

If an adverse event meets any of the following criteria, it is considered a serious adverse event (SAE):

Death of Patient:	An event that results in the death of a patient.
Life-Threatening:	An event that, in the opinion of the investigator, would have resulted in immediate fatality if medical intervention had not been taken. This does not include an event that would have been fatal if it had occurred in a more severe form.
Hospitalization:	An event that results in an admission to the hospital for any length of time. This does not include an emergency room visit or admission to an outpatient facility.
Prolongation of Hospitalization:	An event that occurs while the study patient is hospitalized and prolongs the patient's hospital stay.
Congenital Anomaly:	An anomaly detected at or after birth, or any anomaly that results in fetal loss.
Persistent or Significant Disability/Incapacity:	An event that results in a condition that substantially interferes with the activities of daily living of a study patient. Disability is not intended to include experiences of relatively minor medical significance such as headache, nausea, vomiting, diarrhea, influenza, and accidental trauma (e.g., sprained ankle).
Important Medical Event Requiring Medical or Surgical Intervention to Prevent Serious Outcome:	An important medical event that may not be immediately life-threatening or result in death or hospitalization, but based on medical judgment may jeopardize the patient and may require medical or surgical intervention to prevent any of the outcomes listed above (i.e., death of patient, life threatening, hospitalization, prolongation of hospitalization, congenital anomaly, or persistent or significant

disability/incapacity). Additionally, any elective or spontaneous abortion or stillbirth is considered an important medical event. Examples of such events include allergic bronchospasm requiring intensive treatment in an emergency room or at home, blood dyscrasias or convulsions that do not result in inpatient hospitalization, or the development of drug dependency or drug abuse.

11.1.2 Severity

The following definitions will be used to rate the severity for any adverse event being collected as an endpoint/data point in the study and for all serious adverse events.

Mild:	The adverse event is transient and easily tolerated by the patient.
Moderate:	The adverse event causes the patient discomfort and interrupts the patient's usual activities.
Severe:	The adverse event causes considerable interference with the patient's usual activities and may be incapacitating or life threatening.

11.1.3 Relationship to Pharmaceutical Product

The following definitions will be used to assess the relationship of the adverse event to the use of product:

Reasonable Possibility	An adverse event where there is evidence to suggest a causal relationship between the product and the adverse event.
No Reasonable Possibility	An adverse event where there is no evidence to suggest a causal relationship between the product and the adverse event.

If no reasonable possibility of being related to product is given, an alternate etiology must be provided for the adverse event.

11.1.4**Serious Adverse Event Collection Period**

Serious adverse events will be reported to AbbVie from the time the physician obtains the patient's authorization to use and disclose information (or the patient's informed consent) until 30 days or 5 half-lives following the intake of the last dose of physician-prescribed treatment.

11.1.5**Serious Adverse Event Reporting**

In the event of a serious adverse event, the physician will:

- For events from patients using an AbbVie product - notify the AbbVie contact person identified below within 24 hours of the physician becoming aware of the event.

**11.1.6****Pregnancy Reporting**

In the event of a pregnancy occurrence in the patient, the physician will notify AbbVie contact person identified in Section 11.1.5 within 24 hours of the physician becoming aware of the pregnancy.

11.1.7**Malignancy Reporting**

In the event of any non-serious event of malignancy in subjects 30 years of age and younger, whether related to adalimumab or not, the investigator will notify AbbVie Emergency contact person identified at the beginning of the protocol within 24 hours of the site being made aware of the event.

Adalimumab therapy has a well-established and well described safety profile based on extensive postmarketing experience and continued clinical trial patient exposure since the first approved indication in 2002 for rheumatoid arthritis. A detailed discussion of the pre-clinical toxicology, metabolism, pharmacology and safety experience with adalimumab can be found in the current Investigator's Brochure. AbbVie is committed to continue to collect safety information including those events that may occur in this trial in order to

confirm this established safety profile and to identify any unknown potential adverse reactions, rare events and those events with a long latency. AbbVie is participating in an FDA-requested, TNF inhibitor class wide exploration of the rare appearance of malignancy in subjects/patients who are 30 years of age or younger at the time of diagnosis. The risk of malignancy in this age group has not been established and is difficult to study due to its rarity. AbbVie appreciates your attention to the additional reporting requirements needed in this unlikely event, outlined in Section 11.7 under Malignancy Reporting.

11.2 Product Complaint

11.2.1 Definition

A Product Complaint is any Complaint (see Section 11.0 for the definition) related to the biologic or drug component of the product or to the medical device component(s).

For a product this may include, but is not limited to, damaged/broken product or packaging, product appearance whose color/markings do not match the labeling, labeling discrepancies/inadequacies in the labeling/instructions (example: printing illegible), missing components/product, device not working properly, or packaging issues.

For medical devices, a product complaint also includes all deaths of a patient using the device, any illness, injury, or adverse event in the proximity of the device, an adverse event that could be a result of using the device, any event needing medical or surgical intervention including hospitalization while using the device and use errors.

Any information available to help in the determination of causality by the device to the events outlined directly above should be captured.

11.2.2 Reporting

Product Complaints concerning the investigational product and/or device must be reported to the Sponsor within 24 hours of the study site's knowledge of the event via local Product Complaint reporting practices. Product Complaints occurring during the study will be followed-up to a satisfactory conclusion. All follow-up information is to be reported to the Sponsor (or an authorized representative) and documented in source as required by the

Sponsor. Product Complaints associated with adverse events will be reported in the study summary. All other complaints will be monitored on an ongoing basis.

Product complaints involving a non-Sponsor investigational product and/or device should be reported to the identified contact or manufacturer, as necessary per local regulations.

Product Complaints may require return of the product with the alleged complaint condition (syringe, pen, etc.). In instances where a return is requested, every effort should be made by the investigator to return the product within 30 days. If returns cannot be accommodated within 30 days, the site will need to provide justification and an estimated date of return.

The description of the complaint is important for AbbVie in order to enable AbbVie to investigate and determine if any corrective actions are required.

12.0 Ethical and Legal Consideration

All participant data will be handled in a manner compliant with all local regulatory and privacy laws. All parties will ensure protection of subject personal data and will not include subject names on any sponsor forms, reports, publications, or in any other disclosures, except where required by law. Appropriate role-based access to minimum necessary information will be maintained so that only authorized individuals have access to protected health information (PHI).

AbbVie shall comply with all applicable laws regarding the reporting of spontaneous adverse events (AEs) to the relevant local authorities in Korea. AbbVie will follow the International Conference on Harmonization of Good Clinical Practice (ICH-GCP) guidelines for AE reporting and report all spontaneously reported AEs within the required timeframe (usually within 24 hours of discovery).

All IMS staff working directly with patient data and/or having direct contact with healthcare practitioners will have received formal training to ensure they have a clear understanding of how to recognize an AE and inform Affiliate Safety Specialist so that they are in full compliance with local laws regarding AE reporting.

The study will be reviewed and approved by the appropriate Ethics Committee(s) at each site prior to the start of patient recruitment, according to the specific legal requirements in each country.

13.0 Confidentiality

13.1 Patient confidentiality

Information on patients' identity shall be considered as confidential for all effects and purposes. Each site and patient will have a code in the study. Sites will be automatically coded by IMS. Patients will be assigned a sequential number by the site coordinator upon meeting all inclusion and no exclusion criteria.

The patients' identity should not be revealed nor published under any circumstances. Patient data recorded in the CRF will be documented anonymously, coded with a patient number in such a way that only the investigator and site staff may associate particular data with an identified or identifiable individual or his/her medical record. All other parties involved in data management, analysis and storage will receive, and subsequently analyze, non-identifiable patient data.

13.2 Data confidentiality

By signing the investigator's confidentiality agreement, the investigator affirms to AbbVie/IMS that information furnished by AbbVie/IMS to the investigator will be kept in confidence and such information will be divulged to any expert committee, affiliated institution, and employees only under an appropriate understanding of confidentiality with such committee, affiliated institution and employees.

14.0 Study administration

The entire study will be managed by an international project coordinator at IMS Japan K.K. who will coordinate the project and maintain fluid communication with the study sponsor, the study team and the director at IMS Japan K.K.

As part of the monitoring plan, regular phone calls (at least every two weeks) will be made between IMS and local site coordinator in order to check inclusion status, resolve any issues, check data plausibility, etc.

15.0 Investigators compliance

By signing the investigator's agreement, the investigator agrees to conduct the study in an efficient and diligent manner and in conformance with this protocol, generally accepted standards of good clinical practice and all applicable laws, rules and regulations relating to the conduct of the study.

The investigator shall prepare and maintain complete and accurate study documentation in compliance with applicable national and local laws, rules and regulations and, for each patient participating in the study, promptly record all data in the CRF as required by this protocol.

16.0 Risks

This is a non-interventional observational study. It does not involve any direct patient intervention with respect to laboratory tests, examinations or drug treatment. Patients will be asked to complete questionnaires related to their RA, QoL, functioning, work productivity, treatment satisfaction, and healthcare resource utilization at their clinic during their visit three times over the course of 6 months, requiring approximately 30 minutes of their time each time.

17.0 Discontinuation or Drop-out

Patients' participation in the study is completely voluntary, and they are allowed to withdraw or discontinue from the study. The following three situations will be counted as study drop-out:

- 1) Patient is switched off Adalimumab
- 2) Patient is not willing to continue participation in the study
- 3) Patient disappears and cannot be contacted anymore

For the first two situations, the Early Termination Form (Appendix K) will be provided for the patients and their physicians to fill in.

Patients not completing questionnaires will not be classified as drop-out. For example, if a patient missed Week 12 questionnaires for some reason, he/she can still fill in Week 24 questionnaires.

Once a subject is dropped out from the study, no further information for that subject will be collected. However, the reason for drop-out will be collected and, if the reason for treatment discontinuation is due to an adverse event, the event will be reported as follows :

- SAE : reported to Abbvie within 24 hours of physician awareness

- Non-serious AE : reported to Abbvie within 24 hours of PMOS physician awareness.

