9.0 Research Methods

9.1 Study Design

This study is designed as a prospective, observational study to assess the effect of adalimumab on health-related QoL and work productivity in patients with RA in Korea in clinical practice.

Note: This study is non-interventional and the subjects/investigators will follow the current clinical practice in each site and also the routine clinical follow up as determined by the treating physician.

RA patients will be recruited from within the clinical settings of each rheumatologist participating in the study. Approximately 89 patients diagnosed with RA that meet the inclusion and exclusion criteria will be enrolled at approximately 9 sites in Korea.

To assess health and disability outcomes, the HAQ DI will be assessed at baseline, Week 12 and Week 24 after treatment initiation with adalimumab. In addition, other PROs of work activity and well-being, including the WPAI, EQ-5D, and SF-36, will also be assessed.

The patients identified by the recruiting investigators (specialty dependent on country/region; e.g. rheumatologist, internists, general practitioners, etc.) based on the study selection criteria will complete a set of patient questionnaires on QoL, functioning, work productivity, treatment satisfaction, impression of change and HCRU. Data will be captured at baseline (D0), Week 12 and Week 24.

The HCRU will also be collected. This includes surgical procedures, hospitalizations, bed days in hospital, physician consultations etc. Costs will be assigned based on the HCRU using standardized costs for each participating countries.

Subjects may discontinue adalimumab treatment at any time during study participation. Subjects that end study participation early will have a Termination Visit. All subjects will have a follow-up phone call approximately 70 days after the last administration of adalimumab to obtain information on any new or ongoing AEs.

This protocol requires all SAEs and AESIs as outlined in protocol section 11.0 to be actively solicited. The safety profile of adalimumab which has over 3.5 million patient years of post-marketing exposure is stable and well established; non-serious events will not be actively solicited as these events are not likely to contribute to the further understanding of the safety profile of the product. Any non-serious AEs will be collected as spontaneous reports if AbbVie is notified.

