9.1.1 Schedule of Events

Table 1 Study Activities (Day 1/Baseline Through 6 months)

	Study Activity	Baseline ^a	Week 12 (V2) ± 7 days	Week 24 (V3) ± 7 days	Early Termination / Drop out
Clinician Packet	Inclusion/exclusion form	X			
	Clinical history/patient demographics	X			
	Comorbidities	X			
	DAS28 (ESR) or DAS28 (CRP)	X	X	X	X
Patient Packet	EuroQoL 5-Dimension (EQ-5D)	X	X	X	X
	Short Form 36-Item Health Survey (SF-36)	X	X	X	X
	Health Assessment Questionnaire (HAQ)	X	X	X	X
	Work Productivity and Activity Impairment Questionnaire (WPAI)	X	X	X	X
	Healthcare Resource Utilization (HCRU)	X	X	X	X
	Patient Global Impression of Change (PGIC)		X	X	X
	Patient Treatment Satisfaction Questions	X	X	X	X
	Adverse events (including malignancy)	X	X	X	X

a. The Baseline visit date will serve as the reference for all subsequent visits. A ± 7 day window is permitted around scheduled study visits.

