9.7.6 Additional Secondary Endpoint Analysis

Additional efficacy analysis includes:

- Change in HAQ DI score at 24 weeks after the initiation of adalimumab, in those patients continuing on adalimumab, compared with those patients not continuing on adalimumab. The mean changes in these two groups will be compared using an independent t-test.
- Healthcare resource utilization will be described using number and percentage within each category (number of consultations, number of procedures received, number of surgeries, number of hospitalizations and length of stay, number of concomitant medications)
- Associations between disease severity and PROs
- Associations between change in disease severity and change in PROs

Exploratory endpoint

Change in patient satisfaction questions at weeks 12 and 24 after the initiation of adalimumab (observed population). These changes will be summarized as number and percentage of each response and compared with Kruskal-Wallis test. Satisfaction will also be dichotomized and analyzed over time with Cochrane-Armitage test for trends.

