9.7.9 Missing Data

Efficacy measures are not assessed after a participant discontinues adalimumab. The exception to this will be the analysis of proportion of patients at 24 weeks who remain on adalimumab. Item level data on the PROs will be imputed according to the developers' recommendations. There will be no other imputation for missing data.

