7. Since you last filled out this questionnaire, when you were hospitalized in relation to your rheumatoid arthritis, how many days did you stay at the hospital for your rheumatoid arthritis		
 No hospitalization since you last filled out this questionnaire		
Most recent hospitalization Admission date: _____ / _____ / _____ (DD/MM/YYYY)	 Intensive care unit (ICU)  General ward  Both  Other: _____	 Total days in hospital
Next hospitalization Admission date: _____ / _____ / _____ (DD/MM/YYYY)	 Intensive care unit (ICU)  General ward  Both  Other: _____	 Total days in hospital
Next hospitalization Admission date: _____ / _____ / _____ (DD/MM/YYYY)	 Intensive care unit (ICU)  General ward  Both  Other: _____	 Total days in hospital

8. Please answer the questions below.		
A) Do you need assistance with your daily tasks?	 No  Yes	
B) Do you have a caregiver or somebody to assist you day-to-day?	 No  Yes	
C) Have you made any modifications to your home due to your rheumatoid arthritis?	 No  Yes	

Thank you for completing the Healthcare Resource Utilization Questionnaire.
 Please return this form to the IMS representative.

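### The planned 24-week HAQ DI comparison of continuers with non-continuers has no defined value for the non-continuers, because Section 17.0 ends data collection when adalimumab stops

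*Protocol*

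**What the plan says.** Section 17.0 of the protocol lists three kinds of study drop-out. The first is "Patient is switched off Adalimumab"; the others are unwillingness to continue and loss of contact. It then states: "Once a subject is dropped out from the study, no further information for that subject will be collected". The exceptions given are the reason for drop-out and, where an adverse event caused the stop, the report of that event. For the first two kinds, "For the first two situations, the Early Termination Form (Appendix K) will be provided for the patients and their physicians to fill in".

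The schedule in Section 9.1.1 (Table 1) has a column headed "Early Termination / Drop out". It marks HAQ, SF-36, EQ-5D, WPAI, HCRU, PGIC, the satisfaction questions and DAS28.

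Section 9.7.9 says "Efficacy measures are not assessed after a participant discontinues adalimumab", and SAP 3.5.5 repeats the sentence. Section 9.7.9 allows imputation only for PRO items; the SAP adds only missing days in dates.

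Section 9.7.6 plans the 24-week HAQ DI change in patients who continue, "compared with those patients not continuing on adalimumab", tested with an independent t-test. The Abstract, Section 9.1, and SAP 2.3, 5.3 and Table 3.2 carry the same comparison.

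**The concern.** The analysis sections ask for a 24-week outcome in patients who stopped adalimumab, while the conduct sections end collection when they stop. Unless this is resolved, the second arm of the t-test is empty, or it is filled with values from other time points chosen after the data are seen.

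A secondary matter is what is collected at termination. Table 1 schedules the full set of questionnaires, whereas Section 17.0 names only Appendix K, whose patient part closes with "Thank you for completing the Healthcare Resource Utilization Questionnaire". Sites could read this in different ways.

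What is at stake is selection, not precision. SAP 3.5.5 itself says that missing data in this study cannot be taken as missing at random. If patients who stop do worse, the reported change describes only those who stayed on the drug, and the one planned analysis that could show the difference cannot be run.

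**Working it through.** **The plan's own figures.** Section 9.5 uses one-sided alpha 0.05 and power 0.80, with n = (SD × (z₁₋α + z₁₋β) / Δ)².
- HAQ DI: (0.5 × (1.645 + 0.842) / 0.21)² ≈ 35.1, rounded up to 36.
- WPAI: (25 × 2.487 / 9.9)² ≈ 39.4, rounded up to 40.
- Enrolment: 40 / 0.5 / (1 − 0.1) = 88.9, so 89.

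All three reproduce, and none depends on this point.

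**What a patient who stops contributes.** Take a patient who stops between the Week 12 and Week 24 visits.
- Baseline and Week 12 HAQ DI: collected before stopping.
- Termination HAQ DI: scheduled by Table 1, timed at stopping.
- Week 24 HAQ DI: not collected under Section 17.0. The exception is a termination visit that falls within the ±7 days Table 1 allows around Week 24.
- Substitute for Week 24: none. No section lets the termination value stand in, and imputation at that level is excluded.

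A patient who stops before Week 12 lacks the Week 12 value as well.

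**How many.** 0.10 × 89 = 8.9, about 9 patients. This is a ceiling at the planned rate, because the 10% covers all three kinds of drop-out and only the first is created by the rule on stopping the drug. The documents do not split the 10%.

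**Primary analysis.** With 80 continuers, a change of −0.21 and SD 0.5, the two-sided paired t-test at 0.05 has noncentrality 0.42 × √80 = 3.76 and power of about 96%.

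**The comparison if Week 24 were fully collected.** Assume all drop-outs are non-continuers (80 against 9), SD 0.5, and a between-group difference of 0.21. The documents state no such difference.
- SE = 0.5 × √(1/80 + 1/9) = 0.176.
- Two-sided power is about 22%.
- Difference detectable with 80% power: (1.96 + 0.842) × 0.176 = 0.49.
- With drop-out assumed between 5% and 30% (4 to 27 non-continuers), power runs from 13% to 44% and the detectable difference from 0.72 to 0.32.

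**Possible selection.** Assume continuers change by −0.21.

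| Assumed change in non-continuers | All-starter mean, 9 of 89 stop | All-starter mean, 27 of 89 stop |
|---|---|---|
| 0 | −0.21 × 80/89 = −0.189 | −0.21 × 62/89 = −0.146 |
| +0.21 | −0.21 × (80 − 9)/89 = −0.168 | −0.21 × (62 − 27)/89 = −0.083 |

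These figures are illustrations; the documents give no outcome for patients who stop.

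**The case against.** The other side has several good points.

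- **Termination HAQ DI.** A reader might infer that none is taken, because Appendix K contains none. The documents do not support that. Appendix K is the termination counterpart of the follow-up CRF and the follow-up HCRU form, and those hold no PROs either. Section 9.2.4.7 says the HCRU form goes out together with the separate PRO instruments, and Table 1 marks HAQ at termination. Section 17.0 does not say that Appendix K replaces the rest. The likely reading is Appendix K plus the Table 1 questionnaires, so this is a wording problem.
- **Section 9.7.9.** It sits in the analysis chapter and speaks of the time after stopping. It does not cancel the scheduled termination assessment.
- **Section 9.1 against 17.0.** "Subjects may discontinue adalimumab treatment at any time during study participation" can be read consistently with Section 17.0: stopping happens during participation and triggers termination. The two sit uneasily but do not plainly conflict.
- **Nine patients missing by rule.** That also overreads the plan. Patients who withdraw or are lost would lack Week 24 data under any rule.
- **No later estimate possible.** This is too strong. Baseline, any Week 12 value and the termination value would support an estimate that rests on assumptions.
- **On-drug primary analysis.** This is a legitimate choice, and nothing here requires changing it.

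What survives is that a termination value is taken at stopping, not at Week 24, and the plan gives no rule for using it. None of the replies supplies the missing definition.

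**Conclusion.** The point holds in this form. A patient switched off adalimumab normally has no Week 24 HAQ DI, and the comparison in Section 9.7.6 and SAP Table 3.2 cannot be produced as defined. At the planned drop-out rate it affects at most about 9 of 89 patients, and fewer once withdrawals and losses to contact are removed.

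It touches an additional secondary analysis that would be weakly powered even with complete data: about 22%, on the assumed 0.21 difference, SD 0.5 and an 80 to 9 split. The primary test is not threatened. The reason to act is that a planned analysis lacks its data and that the selection it was meant to describe would go unseen. The termination wording in Section 17.0, Table 1 and Appendix K should be aligned, but it is not evidence that termination HAQ DI values are absent. This should be corrected; it does not invalidate the study.

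**What to change.** The changes concern data collection and analysis only, not any decision about treatment.

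1. In Section 17.0, separate stopping adalimumab from leaving the study. Patients who stop but still consent complete the Table 1 patient packet at the routine Week 12 and Week 24 visits.
2. Remove the matching sentence from both Section 9.7.9 and SAP 3.5.5, and reword the exception that follows it.
3. State in Section 17.0 that the termination packet is the Table 1 PROs plus Appendix K.
4. Keep the on-drug primary analysis. Flag values taken after stopping and report them separately.
5. Where Week 24 values can no longer be obtained, redefine Section 9.7.6, SAP 2.3 and 5.3, and Table 3.2 on the termination-visit HAQ DI. Report its timing and the number of non-continuers who contribute. This fallback may be the practical route: Section 6.0 puts the end of data collection at 28 February 2018, and the approvals of Amendment 01 are dated March and April 2018.

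The cost is a protocol and SAP amendment, plus about 30 minutes of questionnaires (Section 16.0) at up to two routine visits for at most about 9 patients. The downside is that values after stopping partly reflect the next therapy, which is why they are reported apart. Given the low power, the comparison is best presented as an estimate with its confidence interval.

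### Protocol 17.0 ends data collection when a patient comes off adalimumab, against the 70-day adverse event call in 9.1 and the post-dose SAE period in 11.1.4, and the SAP contains no adverse event analysis

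*Protocol*

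**What the plan says.** **Collection.** Protocol 17.0 lists three situations that count as study drop-out. The first is "Patient is switched off Adalimumab"; the third is "Patient disappears and cannot be contacted anymore". For early leavers it provides a form: "For the first two situations, the Early Termination Form (Appendix K) will be provided for the patients and their physicians to fill in". It then states: "Once a subject is dropped out from the study, no further information for that subject will be collected". The one exception that follows is that "the reason for drop-out will be collected and, if the reason for treatment discontinuation is due to an adverse event", that event is reported.

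Protocol 9.1 covers the same patients differently. It says "Subjects that end study participation early will have a Termination Visit", and then: "All subjects will have a follow-up phone call approximately 70 days after the last administration of adalimumab". The purpose of that call is to ask about adverse events, whether new or still continuing. It also requires SAEs and AESIs to be actively solicited. Section 11.1.4 keeps SAE reporting open until 30 days or five half-lives after the last dose. Section 9.7.9 stops only efficacy measures once a patient discontinues.

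**Analysis.** Protocol 9.7.7 opens with adverse events that occur on adalimumab. It then plans incidence summaries of AEs and SAEs by System Organ Class, severity and relatedness, with no time window in that sentence. Section 9.7.1 says the SAP will include the analyses described in the protocol and will govern all analysis. The SAP names spontaneous adverse events as collected data (3.3.1) and keeps CTCAE and SOC in its abbreviations (7). It describes no safety analysis in 5.1 to 5.6 and lists no safety table in 6.

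**The concern.** A patient switched off adalimumab falls under 17.0, 9.1 and 11.1.4 at once. Section 17.0 tells the site to stop; the other two tell it to carry on. A site that follows 17.0 would not make the call and could miss SAEs and AESIs that begin after the switch, together with other new events the call would have revealed. Section 11.1.7 gives one purpose of the safety data as finding rare events and events with long latency, so the period after the last dose matters to the sponsor's own stated aim.

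At the analysis stage, new events after the last dose have no assigned place, and output built from the SAP text would contain no adverse events at all.

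**Working it through.** The conflict is textual, so the sections are set side by side. The only arithmetic concerns scale, table counts and dates.

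**1. What a site collects after a switch**

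| Item | 17.0 | Elsewhere in the protocol |
|---|---|---|
| Early termination form or visit | Kept | Required (9.1; Table 1 marks adverse events there) |
| Reason for drop-out | Kept | – |
| AE that caused discontinuation | Kept | – |
| 70-day call for new or ongoing AEs | Not excepted | Required for all subjects (9.1) |
| New SAE after the last dose | Not excepted | Reportable (11.1.4), within 24 hours of awareness (11.1.5) |

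The last two rows conflict. Section 17.0 neither refers to section 11 nor mentions the call. It is also broader than 9.7.9 needs, since that section stops efficacy measures only.

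**2. Which events 9.7.7 covers**

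- Began on drug, still ongoing at the call: covered, because it occurred on adalimumab.
- Began after the last dose: unclear. The first sentence is limited to time on drug; the incidence sentence states no window.
- Section 11.1.4 does not settle it, because it offers two limits without saying which governs. The documents give no half-life. If it were 70/5 = 14 days (an assumption), five half-lives would end at the 70-day call; the alternative ends at 30 days. The two limits would then differ by 70 − 30 = 40 days.

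**3. SAP tables**

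Section 6 lists 1, 2, 3.1, 3.2, 4, 5, 6, 7, 8, 9.1, 9.2 and 10, which is 12 tables. AE or SAE tables: 0. Table 8 covers RA-related resource use only.

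**4. Scale**

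The planned size reproduces: 40/0.5/(1 − 0.1) = 88.9, rounded up to 89 (protocol 9.5). At the planned 10% drop-out, 89 × 0.10 = 8.9 patients leave for any of the three reasons. This is neither a bound nor a count of missed events: 10% is a planning assumption, drop-outs are not split by reason, and no AE rate is given.

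**5. Timing**

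Inputs: planned end of collection 28 Feb 2018 and final report 31 Aug 2018 (protocol 6.0); Amendment 01 dated 26 Dec 2017 (5.0), with approval dates from 3 Mar to 12 Apr 2018.

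- Amendment date to end of collection: 64 days.
- End of collection to approvals: 3 to 43 days.
- Approvals to final report: 181 down to 141 days.

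On the approval dates, edits to collection may come too late, while the analysis edits still have time.

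**The case against.** The best defence is that 17.0 closes CRF and questionnaire collection and leaves safety to section 11. Section 9.1 deals with discontinuers directly and says the call applies to all subjects. Section 9.2.4 sends adverse event procedures to section 11, 11.1.4 ties SAE reporting to the last dose rather than to study participation, and the 24-hour duty remains. That makes loss of events a risk, not a certainty. It does not remove the conflict: 17.0 bars all further information and then lists narrow safety exceptions, which would be unnecessary if safety already lay outside the sentence.

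Other points have some force:

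- Outside the call, 9.1 leaves non-serious events to spontaneous reports by design, so that limit is not a result of 17.0.
- Table 1 is titled as running to 6 months. For a patient dosed to Week 24 the call falls after that; it falls inside 24 weeks only if the last dose is by day 168 − 70 = 98. Adding it there is a clarification.
- Limiting a safety summary to on-drug events is a legitimate choice. The fault is that 9.7.7 does not state it for the incidence summaries, while 9.1 orders a call to find new events.
- The SAP gap is separate from 17.0 and would remain if 17.0 were corrected. The SAP is version 0.2, says tables may be modified, and refers to a table-shell workbook that is not among the documents. A safety shell could exist there, but the SAP text has no analysis for it to serve.

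**Conclusion.** The concern holds. As written, 17.0 cannot be followed literally together with 9.1 and 11.1.4, and the SAP omits the AE and SAE summaries that 9.7.7 plans and 9.7.1 says it will include: 0 of 12 listed tables. New events after the last dose are not clearly covered by 9.7.7. The two substantive faults are the wording of 17.0 and the missing SAP analysis; the Table 1 entry, the single window in 11.1.4 and the separate post-dose display are clarifications.

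The number of patients or events affected cannot be estimated from the documents. Confidence is high on the text and lower on the consequence, which depends on which rule sites followed and on what the unseen workbook contains. The change should be made, but the HAQ DI analysis does not depend on it.

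**What to change.** 1. **Protocol 17.0:** limit the sentence to efficacy and questionnaire data. State that section 11 safety reporting and the 70-day call continue unless the patient withdraws consent to contact or cannot be reached.
2. **Table 1:** add the call.
3. **Protocol 11.1.4 and 9.7.7:** state one post-dose window and use it in both. Show new post-dose events separately from on-drug events, because a switched patient may be taking another drug.
4. **SAP 5 and 6:** add an AE/SAE analysis and table by System Organ Class, severity and relatedness, as 9.7.7 plans.

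The cost is wording in three protocol sections, one Table 1 row and one SAP table, with no patient contact beyond the call 9.1 already requires. If collection has closed, make only the 9.7.7 and SAP changes and state in the report which collection rule sites followed.
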